We will construct a mixed effects generalized linear model that will act on data aggregated monthly within each provider to estimate the average intervention effect across providers. We will use a Poisson outcome model with a log link to characterize each provider’s monthly rate, where the number of positive screens will be the outcome and the log of the number of total screens will be included as an offset term.^{53,54} In the case of over-dispersion, we will use a negative binomial outcome model. The main predictor of interest will be a pre/post indicator for whether the report card intervention was in effect at a particular month (Intervention). We will additionally control for time since the study began in quarters (Time, coded as a categorical variable) to account for secular trends; as well as site level characteristics obtained from administrative and the quantitative survey data (Aim 1) (urban/rural, cumulative annual procedure volume in 2018 and current volume, site annual ADRs in 2018, use of split dose bowel preparation protocols (SDBP) in 2018, and whether or not ADR was measured in 2018), provider level characteristics (baseline years in practice, primary practice type {academic, hospital employed, private practice}, and baseline annual procedure volume), and baseline patient characteristics aggregated to the provider level (age, sex, race/ethnicity). Since study time will be coded in quarters, it will incorporate seasonal effects in addition to secular trends over the study period. Random effects will be included for both provider and site, where provider is nested within site. Let $PositiveScreens_{ijt}$ denote the observed number of positive screens for the j th provider at site i during month t , and let $TotalScreens_{ijt}$ denote the total number of patients screened. Because the monthly screening rates are expected to be relatively low (≤ 0.30), we assume that the observed number of positive screens, $PositiveScreens_{ijt}$ follows a Poisson distribution with conditional mean λ_{ijt} . We anticipate the following model for λ_{ijt} on a log scale, where $TotalScreens_{ijt}$ is included as an offset term on the right hand side of the equation: $\text{Log}(\lambda_{ijt}) = \beta_0 + \beta_1 Intervention_{ijt} + \beta_2 Time_{ijt} + \beta_3 Urban_i + \beta_4 SiteVolume_i + \beta_5 YrsPractice_{ij} + \beta_6 PracticeType_{ij} + \beta_7 ProviderVolume_{ij} + \beta_8 Age_{ij} + \beta_9 Sex_{ij} + \beta_{10} Race_{ij} + \beta_{11} Volume2018_i + \beta_{12} ADR2018_i + \beta_{13} SDBP2018_i + \beta_{14} ADRMeasured_i + \alpha_i + \mu_{j(i)}$, where β_0 is the intercept, β_2 is a vector of coefficients for the study quarter as expressed by $Time_{ijt}$, α_i indicates the random effect for site i , $\mu_{j(i)}$ indicates the random effect for provider j within site i . $Volume2018_i$ (high/low), $ADR2018_i$ (high/low) and $ADRMasured_i$ (yes/no) are the indicator variables used in stratifying the baseline randomization of sites to waves. We will also examine whether the intervention effect varies by time since intervention and by provider characteristics by considering these interaction terms in the model. Under the proposed Poisson model and logarithmic link function, exponentiating the results will allow us to report rate ratios (RRs), their 95% confidence intervals (CIs), and p-values from the models. Under the generalized linear mixed model the estimated treatment effect, obtained by exponentiating the estimate of β_1 , represents the ratio of the screening rate after versus before implementing the intervention for a given provider.

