
We will plot monthly ADRs for a random sample of endoscopists to examine how the ADR rate changes over time, and to check for the presence of a lagged intervention effect. We expect to see about a one month lag in the intervention effect and plan to drop the outcome data for this period to avoid biased estimates.⁵⁵ We will

examine correlation between successive monthly ADR rates within providers using residual plots and the Durbin-Watson or Durbin's alternative test and include study time lags as appropriate.⁵⁶ If these analyses suggest that the residual covariance deviates substantially from those assumed by the nested random effects model, we will substitute a generalized estimating equation (GEE) analysis under the assumption that outcomes are independent between sites, and use robust standard errors for statistical inference.⁵⁷ The GEE approach can also be used as a fallback if the nested random effect structure of the generalized linear mixed model turns out to be numerically intractable. [As a secondary question we will assess the impact of compliance with the intervention on ADR rate among the providers from Aim 2 who responded to our survey. Compliance will be measured in Aim 1 by dashboard access and participation in one or more collaborative learning sessions. Compliance will be modeled as an interaction with intervention in the model described above, to see if the efficacy of the intervention varies by compliance status.]

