Secondary Analysis -- Interrupted Time-Series (ITS) at the Provider Level: While the analysis described above will be considered primary, our stepped wedge design coupled with our focus on provider performance provides opportunity for several analysis options. As a secondary analysis, we will estimate the average intervention effect across providers using a two-stage approach. In the first stage, we will implement ITS models within each provider, estimating the intervention effect for each provider. In the second stage, we will use a meta-regression approach to combine results across providers to estimate the mean and the standard deviation (on the log scale) of the intervention effect across providers.^{61,62} This analysis is conventional for pre/post analysis of interventions implemented at different time points for different units,^{62,63} and has the advantage of evaluating both the overall intervention effect and the heterogeneity in the treatment effect across sites and providers. However, it focuses on pre/post comparisons within providers and does not allow for comparisons between treatment and control at the same time points as is done in our stepped wedge analysis.

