The first stage ITS analysis will consist of segmented regression with an autoregressive error model to account for the correlation between successive monthly ADRs. As described in the primary analysis, we will plot monthly ADRs for a random sample of endoscopists to guide our ITS modelling strategy. We will also use these plots to assess whether to include seasonal effects, which would be included as a categorical quarter variable in the model. We assume that a provider's observed number of positive screens during month t , $PositiveScreens_t$, follows a Poisson distribution with conditional mean λ_t . Our basic ITS model for λ_t for a particular provider has the following form: $\text{Log}(PositiveScreens_t) = \beta_0 + \log(TotalScreens_t) + \beta_1 Intervention_t + \beta_2 Time_t + \beta_3 Time\text{-}After\text{-}Intervention_t + \beta_4 Age + \beta_5 Sex + \beta_6 Race + \beta_7 Season_t$, where t indicates time coded in months.⁵⁵ In this ITS analysis, time is coded monthly and treated as a continuous variable instead of coding it as a categorical variable as in the stepped wedge analysis. The main predictors of interest will include the immediate intervention effect (*Intervention*) and whether the monthly post-intervention time trend differs from the pre-intervention time trend (*Time-After-Intervention*). Autocorrelation will be examined using residual plots and the Durbin-Watson or Durbin's alternative test and corrected using lagged study time variables as appropriate.⁵⁶ Each model will provide a RR estimate, 95% CI and p-value for a provider's intervention effect.

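### The interrupted time-series stage names two autocorrelation remedies: one is void as worded and the other is missing from the printed model, so provider intervals and the between-provider SD are not secured

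*Combined protocol and SAP*

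**What the plan says.** Aim 1, Secondary Analysis (ITS at the provider level), describes the first stage as "segmented regression with an autoregressive error model to account for the correlation between successive monthly ADRs". The equation printed below it is a Poisson log-linear model with an intercept, an offset, Intervention, Time, Time-After-Intervention, patient covariates and season. It has no error, lag or autoregressive term. In that model "time is coded monthly and treated as a continuous variable". Residual plots and a Durbin-Watson type test follow, and any autocorrelation found is to be "corrected using lagged study time variables as appropriate". Each provider model is to give a rate ratio, a confidence interval and a p-value. The second stage is meant to "estimate the mean and the standard deviation (on the log scale) of the intervention effect across providers".

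The Primary Analysis (stepped wedge) works on provider-month rows and adjusts for "time since the study began in quarters (Time, coded as a categorical variable"). After the same kind of residual check it will "include study time lags as appropriate". A fallback follows: "If these analyses suggest that the residual covariance deviates substantially from those assumed by the nested random effects model", the plan moves to generalized estimating equations (GEE), taking sites as independent, and will "use robust standard errors for statistical inference".

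The term for the lagged study-time variables is not defined, and no autocorrelation value is given anywhere.

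**The concern.** Study time is a calendar variable, fixed in advance and the same for everyone. It describes the mean; it carries no information about how one provider's residual in a month depends on that provider's residual in the month before. Adding lags of it cannot do the job assigned to it.

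The autoregressive error model would do that job, but the plan does not say how it enters a Poisson model or what its order is. The later step, which corrects only if a test is positive, would be largely unnecessary if such a term were always fitted. An analyst could follow the section faithfully by fitting the printed equation, running the test and adding lagged time, and would then report uncorrected standard errors.

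At stake are the provider-level intervals and p-values, and the SD of the effect across providers. First-stage standard errors that are too small make the second stage read month-to-month drift as real differences between providers.

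**Working it through.** **1. The plan's own figures.** Inputs from the two Power Calculation paragraphs: 135,517 patients a year, 571 providers, 19.5 months per period, ADR 27.5%, increase 1.25 points.
- Patients per period: 135,517 × 19.5/12 = 220,215. Per provider: 220,215/571 = 385.7. Both match the plan.
- Per provider-month: 386/19.5 = 19.8 colonoscopies, and 19.8 × 0.275 = 5.4 positives.
- Planned effect on the log scale: log(28.75/27.5) = 0.044.
- Stated ITS power of 96.8% needs a standard error of 0.0125/(1.960 + 1.852) = 0.00328 (two-sided 5% assumed). A segmented regression on 20 + 19 months with first-order autoregressive errors gives 0.00328 at correlation 0.3 without the 3-month implementation gap, or at correlation 0.1 with it. The figure is attainable but cannot be confirmed, because the plan's correlation is not stated.

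**2. Lagged time in the ITS model.** Time(t−k) = Time(t) − k, a combination of the intercept and Time. The design (intercept, Intervention, Time, Time-After-Intervention) has rank 4, and still 4 after adding a lag of 1, 2 or 3 months. With season it is 7 and stays 7. In simulated provider fits the mean standard error of the log rate ratio was 0.308 with and without lagged time, and coefficients differed by less than 1e-14.

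**3. Lagged quarters in the primary model.** There are 42 months, or 14 quarters.
- Lag of 3 months: rank 13 before and after (the first quarter is lost). Redundant.
- Lag of 1 or 2 months: rank rises from 14 to 27. Not redundant.
- Lags of 1 and 2 together: rank rises from 14 to 40. Since 42 − 2 = 40 months remain, this is one free level per calendar month, shared by all providers.

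A linear approximation (571 providers, the Figure 5 layout, provider fixed effects, assumed autoregressive provider drift, 150 replicates) shows what those columns do. At drift SD 0.30 and correlation 0.8, the intervention effect had SD 0.026 against a model standard error of 0.017, unchanged by the lags; residual lag-1 correlation went from 0.202 to 0.203. At SD 0.15 and correlation 0.5 the two agreed (0.014 and 0.015).

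**4. If no autoregressive term is fitted in the ITS.** Simulation with 1,500 providers per row, 20 patients a month, ADR 27.5%, no true effect and no true heterogeneity. Drift values are assumptions.

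| Drift SD (log) | Monthly correlation | True SD of estimate | Model SE | 95% CI coverage | Spurious between-provider SD |
|---|---|---|---|---|---|
| 0.1 | 0 | 0.315 | 0.308 | 94.1% | 0.055 |
| 0.1 | 0.3 | 0.323 | 0.307 | 93.9% | 0.096 |
| 0.1 | 0.8 | 0.347 | 0.309 | 92.1% | 0.153 |
| 0.2 | 0 | 0.347 | 0.308 | 92.5% | 0.152 |
| 0.2 | 0.3 | 0.368 | 0.308 | 89.6% | 0.193 |
| 0.2 | 0.8 | 0.436 | 0.310 | 82.9% | 0.296 |
| 0.3 | 0 | 0.380 | 0.309 | 89.5% | 0.216 |
| 0.3 | 0.3 | 0.429 | 0.310 | 85.1% | 0.291 |
| 0.3 | 0.8 | 0.511 | 0.315 | 76.9% | 0.388 |

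The rows at correlation 0 are overdispersion alone, so only the rise below them is due to serial correlation. At SD 0.1 and correlation 0.3 to 0.6, the ratio of model SE to true SD is 0.95, an error of about 5%.

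**5. The test as a gate.** With 571 simulated providers, drift SD 0.15 to 0.30 and correlation 0.5 to 0.8, the Durbin-Watson test flagged only 9% to 26% of providers.

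**6. The pooled mean.** With no autoregressive term at all, the random-effects pooled standard error was close to the empirical one in four settings: 0.0147 against 0.0150, 0.0195 against 0.0198, 0.0151 against 0.0154, and 0.0222 against 0.0226.

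**The case against.** A reader might infer that provider standard errors and the heterogeneity SD will be wrong, and that the primary analysis shares the fault. The documents do not support that.

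- The ITS section opens with an autoregressive error model, and the ITS power paragraph assumes autocorrelated errors. The simulation in step 4 omits that term, so it shows what happens if the opening sentence is not carried out, not what the plan sets out to do. This stands, and it makes the harm conditional.
- In the primary model, lags of one or two months are not collinear, and the GEE fallback with robust standard errors comes in the next sentence. This also stands. What remains is that the lags cannot remove provider-specific correlation, and that the fallback depends on an undefined degree of departure.
- The drift SD and correlation are assumed. At the weak end little is lost.
- The phrase may be loose wording for lags of the outcome or residual. The cited source is not available to settle it. If that is the meaning, the text has to say so, because its literal meaning is void.
- The pooled ITS effect is largely protected, and the ITS is a secondary analysis.

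**Conclusion.** The point holds in limited form. For the ITS first stage, the test-triggered remedy is exactly collinear with terms already in the model; this is algebra and needs no assumption. The other remedy is promised but not written into the model. For the primary analysis, lagged quarter indicators cannot serve the stated purpose, whether redundant (whole-quarter lag) or not (one or two months).

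The consequence needs two conditions: autocorrelation is present, and the autoregressive error is not fitted or is inadequate. Then, over drift SD 0.1 to 0.3 and monthly correlation 0.3 to 0.8, coverage of provider intervals falls to between 94% and 77%. The spurious between-provider SD is about 0.1 to 0.4, part of it overdispersion. That exceeds the planned log-scale effect, so a reported SD of this size could not be read as real variation in response among providers. It does not follow that the main trial result is invalid. This should be corrected before the analysis, but it ranks below the defects that threaten the primary conclusion.

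**What to change.** - Delete the lagged study-time wording in both the Primary Analysis and the Secondary Analysis (ITS).
- In the ITS, write the promised first-order autoregressive term into the Poisson equation, for example as a latent month effect. Pool its correlation and variance across providers, because each series is short. Fit it for every provider, without a Durbin-Watson pre-test.
- Do not use Newey-West standard errors on single-provider series. With 39 usable months and 3 lags they were further from the truth than the plain Poisson ones: 0.25 against 0.33 where the true SD was 0.35 (no drift), and 0.30 against 0.34 where it was 0.54 (strong drift).
- In the primary model, report site-clustered robust standard errors whatever the residual test shows.

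The cost is a few sentences in the analysis plan, modest extra programming, and somewhat wider intervals for individual providers. No change to data collection or the trial's conduct is needed.

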The second stage analysis will consist of random effects meta-regression to aggregate the provider intervention effects estimated from the first stage.^{61,62} This model will enable us to estimate the average intervention effect across providers accounting for heterogeneity at both the site and provider level by including random effects for both. We include a random effect for provider because although we have included the majority of the eligible providers in the VA system, we conservatively consider the providers included in our analysis to be a random sample from the full possible set of providers.⁶⁴ Konstantopoulos et al. describe a similar multilevel meta-regression analysis where studies are nested within school districts – here we have providers nested within sites.⁶⁵ Our meta-regression model will adjust for the variables used in the randomization stratification procedure (*Volume2018*, *ADR2018*, and *ADRMeasured*), provider-level variables (baseline years in practice and baseline annual procedure volume), and site level characteristics including [split dose bowel preparation protocols (SDBP) in 2018,] urban/rural and cumulative annual procedure volume.

Power Calculation: Our power calculation for the overall intervention effect is estimated from an ITS model after accounting for 5% data loss at the site level and 8% provider attrition. On average a provider has 19.5 months of data in both the pre-intervention and post-intervention periods. Thus we estimate 386 patients/provider or 220,215 patients seen in each period. Again, the number of patients is included in the power calculation because the number of patients seen by providers greatly affects the power of our design. To estimate power, we simulated ITS data with varying intervention effect sizes adapting code provided by Rozario et al.⁶⁶ Under an ITS model with an autocorrelated error structure, we expect to achieve 96.8% power to detect a 1.25% increase in ADR from a pre-intervention rate of 27.5% (based on 1000 simulations). Power calculations were conducted in SAS v 9.0.

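### The only second-stage ITS model adjusts for effect modifiers, so its site and provider SDs are residual and not the promised SD of the effect across providers, and no rule says how the average is obtained

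*Combined protocol and SAP*

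**What the plan says.** Aim 1, Secondary Analysis -- Interrupted Time-Series at the Provider Level, sets out two stages. The first fits a segmented regression within each provider. The second is a random-effects meta-regression of the provider effects, whose purpose is "to estimate the mean and the standard deviation (on the log scale) of the intervention effect across providers". The section names the evaluation of heterogeneity across sites and providers as an advantage of this analysis.

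One second-stage model is described. It carries random effects for site and provider, and the plan says of it: "This model will enable us to estimate the average intervention effect across providers accounting for heterogeneity at both the site and provider level". On covariates the plan continues: "Our meta-regression model will adjust for the variables used in the randomization stratification procedure" (Volume2018, ADR2018 and ADRMeasured). It adds "provider-level variables (baseline years in practice and baseline annual procedure volume") and site characteristics, namely split-dose bowel preparation in 2018, "urban/rural and cumulative annual procedure volume".

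In the primary model the three stratifiers "are the indicator variables used in stratifying the baseline randomization of sites to waves", coded high/low or yes/no. Neither model mentions centring. For the second stage there is no averaging over the covariate distribution, no fit without covariates, and no rule for combining residual and covariate-explained variance.

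Two other places bear on this. The implementation-strategy overview under Aim 1 expects the greatest gain at low-volume and low-ADR sites. The Analysis Overview expects a larger effect in providers whose ADR is low beforehand.

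**The concern.** In the primary stepped-wedge model these covariates enter as main effects on the level of ADR, and effect modification is examined separately through interaction terms. In the second stage of the ITS analysis the dependent variable is a provider's log rate ratio. The same list placed there no longer adjusts for differences in ADR level: each coefficient states how the intervention effect changes with that covariate.

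Two consequences follow. First, the site and provider variance components describe only the variation that the covariates leave unexplained. That holds under any coding. Second, with indicator and uncentred coding the intercept is the effect for a provider at every reference level with zero years in practice and zero volume. The plan states no other way to extract the average.

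What is at stake is the heterogeneity result, which is a stated reason for running this analysis, and a choice of reference level that would be left until after the data are seen.

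**Working it through.** **The plan's own figures.** The ITS power section's patient counts reproduce: 135,517 × 19.5/12 = 220,215 per period, and 220,215/571 = 385.7, stated as 386 per provider. The planned effect, 27.5% to 28.75%, is a rate ratio (RR) of 1.0455, with log RR ln(0.2875/0.275) = 0.0445. The stated 96.8% power is plausible: a pooled segmented Poisson model at two-sided 0.05 (assumed) gives 97.1% to 97.7% without autocorrelation and 94.7% to 95.7% with an assumed lag-1 correlation of 0.1. None of these figures depends on the second-stage covariates.

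**Formulas.** Write a provider's effect as θ = β₀ + xβ + site deviation + provider deviation.
- Total variance = Var(xβ) + site variance + provider variance.
- Residual SD = total SD × √(1 − R²), where R² is the share of effect variance that the covariates explain.
- Mean effect = β₀ + mean(x)β. This equals β₀ only if every covariate is centred or β = 0.

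**SD for a given R²** (assumed, since the documents give none). R² of 10%, 25% and 50% gives √0.90 = 0.949, √0.75 = 0.866 and √0.50 = 0.707, so the SD is 5%, 13% and 29% too small.

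**One modifier.** Assume ADR2018 splits providers half and half, the mean log effect is 0.0445, the residual SD is 0.05, and the low-minus-high gap is g. Then total SD = √(0.05² + g²/4), and the intercept is 0.0445 ± g/2 depending on the reference level.

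| g relative to mean effect | Intercept RR, low as reference | Intercept RR, high as reference | Total SD | Residual SD too small by |
|---|---|---|---|---|
| 0.5 (0.0222) | 1.057 | 1.034 | 0.051 | 2% |
| 1 (0.0445) | 1.069 | 1.022 | 0.055 | 9% |
| 2 (0.0889) | 1.093 | 1.000 | 0.067 | 25% |

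**Several modifiers.** A simulation used 571 providers in 69 sites, an ADR gap equal to the mean effect, a volume gap of half that, a slope of −0.001 per year in practice, site SD 0.02 and provider SD 0.05 (all assumed). The true mean RR was 1.046, the uncentred intercept RR 1.092 and the centred intercept RR 1.045. Total SD was 0.060 and residual SD 0.053, about 11% too small. Centring recovers the mean and does nothing for the SD.

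**Would dropping the covariates give the right mean?** Assume log effects of 0.07 at low-volume and 0.02 at high-volume sites, half the providers each, so the provider average is 0.045 (RR 1.046). Under the segmented model the first-stage standard error (SE) is about 0.276 per provider, a variance of 0.0761 at average volume. Assume provider SD 0.05 and site SD 0.025, and weight each provider by 1/(sampling variance + 0.0025 + 0.000625).
- Providers at high-volume sites do twice the procedures: sampling variances 0.0761 × 1.5 = 0.1142 (low) and 0.0761 × 0.75 = 0.0571 (high), weights 8.52 and 16.61. Weighted mean (8.52 × 0.07 + 16.61 × 0.02)/25.13 = 0.037 (RR 1.038).
- Three times: variances 0.1522 and 0.0507, weights 6.44 and 18.56, weighted mean 0.033 (RR 1.033).

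The covariate-free mean therefore leans towards high-volume providers when volume modifies the effect.

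**Scale against noise.** The sampling SE of the between-provider variance is roughly √(2/571) × 0.0761 = 0.0045. The variance omitted in the table is g²/4: 0.0001, 0.0005 and 0.0020.

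**The case against.** The strongest case on the other side has four parts.

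1. The plan never says that the intercept will be reported. It promises an average, and the same fitted model gives that average by centring or by averaging predictions. This stands. A reader might infer that the headline number describes a non-existent provider, with zero years in practice and zero volume. The documents do not support that as a fact, because it depends on a reporting choice not yet made. What is missing is the rule.

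2. The heterogeneity is divided, not lost: coefficients and residual components both come out of the fit. This is also right. A reader might infer that the model removes the heterogeneity it is meant to report; it removes only the covariate-explained part from the random-effect SDs. But the plan does not say that this part will be added back, so the SDs as specified are still not the promised quantity.

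3. The sizes are assumed. The documents expect modification by volume and ADR, but give no magnitude, do not call these the main drivers of differential benefit, and predict nothing for years in practice. All of this stands.

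4. With a first-stage SE near 0.28 per provider, the variance differences in the table lie below the sampling error of the variance estimate. This limits the practical consequence. It does not make a residual SD an estimate of the total SD.

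**Conclusion.** The point holds as a mismatch between a promised quantity and the only model specified to deliver it, within a secondary analysis. The SD half holds under any coding: the site and provider SDs are residual, and understate total heterogeneity whenever a covariate modifies the effect, as the plan expects for volume and ADR. The mean half is narrower: under reference or uncentred coding the intercept is not the provider average, and a rule for obtaining the average is missing.

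The size cannot be derived from the documents. Under the assumptions shown, the SD is 2% to 25% too small for gaps of 0.5 to 2 times the planned effect, and the shortfall is zero without modification. A reader might also conclude that a covariate-free meta-analysis gives the correct mean; under the assumed volume scenario it gives 0.037 or 0.033 against a provider average of 0.045. The primary stepped-wedge analysis and every stated figure are unaffected.

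**What to change.** Change the second-stage paragraph of the ITS section as follows.

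1. Define the average effect as the covariate-model prediction averaged over all analysed providers; centring every covariate at its provider-level mean is equivalent. State that neither the raw intercept nor a covariate-free precision-weighted mean will be reported as the average.
2. Report total site and provider SDs from one additional random-effects fit with the same nesting and no covariates. Alternatively, add the covariate-explained variance to the residual components.
3. Label the site and provider SDs of the covariate model as residual, and use that model to explain heterogeneity.

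The cost is a few sentences and one simpler fit, with no new data. The downside is that total and residual SDs will differ little relative to their sampling error if modification is modest, so both should be reported with intervals.
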